9.2.1.3 Reporting Adverse Events

AEs will be captured on the appropriate subject's source document and eCRF. Information collected for AEs includes event description, time of onset, investigator assessment of severity, relationship to the study drug, date of resolution of the event, seriousness, and outcome.

All AEs will be documented from the time of drug dosing up to and including Final Visit. AEs will be followed to resolution or until considered stable in the clinical judgment of the study investigator. Evaluation of AEs may require unscheduled visits and clinical and laboratory investigations, according to the clinical judgment of the Site PI and study physicians.

9.2.2 Reactogenicity (for Vaccine Studies and Some Therapeutic Trials)

Not applicable.

9.2.3 Serious Adverse Events

An SAE is any AE that meets at least one of the following criteria:

- Death;
- Life-threatening AE*;
- Inpatient hospitalization or prolongation of existing hospitalization;
- Persistent or significant disability or incapacity, or substantial disruption of the ability to conduct normal life function;
- Congenital anomaly/birth defect;
- Important medical events that may not result in death, be life-threatening, or require hospitalization may be considered an SAE when, based upon appropriate medical judgment, they may jeopardize the subject and may require medical or surgical intervention to prevent one of the outcomes listed in this definition. Examples of such medical events include allergic bronchospasm requiring intensive treatment in an emergency room or at home, blood dyscrasias or convulsions that do not result in inpatient hospitalization, or the development of drug dependency or drug abuse.

*Life-threatening AE. An AE is considered “life-threatening” if, in the view of either the investigator or sponsor, its occurrence places the subject at immediate risk of death. It does not include an AE that, had it occurred in a more severe form, might have caused death.

SAEs will be:

- Assessed for severity and relationship to study product and alternate etiology by an authorized study physician (listed on FDA Form 1572);
- Recorded on the appropriate SAE data collection form and eCRF;
- Followed through resolution;
- Reviewed and evaluated by an ISM (as deemed necessary), the SMC (periodic review unless related), DMID, and the IRB.

9.2.4 Procedures to be Followed in the Event of Abnormal Laboratory Test Values or Abnormal Clinical Findings

A licensed study clinician (listed on FDA Form 1572) will make the determination of seriousness, severity, and causality; provide a medical evaluation of AEs; and classify AEs based upon medical judgment.

Abnormal laboratory values or clinical findings for all enrolled subjects, including values and findings noted at screening and baseline, will be assessed using the toxicity scales in [Appendix C](#). Abnormal values and findings noted at screening or baseline will only be considered AEs if

they deteriorate after study drug dosing. For abnormalities noted from the time of study drug dosing, any Grade 1 or higher laboratory abnormality listed on the toxicity table in [Appendix C](#) will be entered in the database as an AE. Safety laboratory results that are abnormal according to the local laboratory reference range, but not considered a Grade 1 abnormality, will be evaluated by the study site clinician and reported as Grade 1 abnormality if clinically significant. If not clinically significant, these will not be considered laboratory AEs and will thus not be graded, but will be recorded in the source document and followed-up clinically at the discretion of the study site clinician. Abnormal laboratory values, performed as part of the complete CBC, clinical chemistry or UA but not listed in this toxicity table will be evaluated by the study clinicians, recorded in the source document and, if clinically significant, considered AEs and graded according to the criteria in [Section 9.2.1](#).

Protocol-specific laboratory normal range values in effect at the time of protocol submission are included in [Appendix B](#). Changes in these ranges during the trial will be handled as administrative protocol amendments and toxicity grades will be calculated using the new ranges from the effective date of the change. A regular protocol amendment will be submitted for these changes if a revised laboratory normal range value meets criteria for Grade 2 toxicity.

Gross blood in urine that is confirmed due to a menstrual cycle is not an AE (but is for all other reasons).

9.3 Reporting Procedures

9.3.1 Serious Adverse Events

SAEs will be followed until resolution even if this extends beyond the study-reporting period. Resolution of an AE is defined as the return to pretreatment status or stabilization of the condition with the expectation that it will remain chronic.

All SAEs will be:

- Recorded on the appropriate SAE report form and sent to DMID Pharmacovigilance Group (PVG)
- Entered into the appropriate subject source document and eCRF in AdvantageEDCSM
- Reported to the Site ISM and the IRB
- Reviewed and followed to resolution or stability by an authorized study physician (listed on FDA Form 1572)
- Collected on each subject until Final Visit

Any AE that meets a protocol-defined serious criterion must be submitted immediately (within 24 h of site awareness) on an SAE report form to DMID PVG:

DMID Pharmacovigilance Group
Clinical Research Operations and Management Support (CROMS)
[name]
[name], USA
SAE Hot Line: [name] (US) or [name] (outside US)
SAE [contact] (US) or [name] (outside US)
SAE Email Address: [contact]

In addition to the SAE report form, selected SAE data fields must also be entered into AdvantageEDCSM. Please see the protocol-specific MOP for details regarding this procedure.

Other supporting documentation of the SAE may be requested by DMID PVG and should be provided as soon as possible.

The site will copy the ISM on SAE reports provided to the DMID PVG. The DMID MM and DMID CPM will be notified of the SAE by the DMID PVG. The DMID MM will review and assess the SAE for regulatory reporting and potential impact on study subject safety and protocol conduct.

At any time after completion of the study, if the site PI or appropriate sub-investigator becomes aware of an SAE that is suspected to be related to study product, the site PI or appropriate sub-investigator will report the event to the DMID PVG.

9.3.2 Regulatory Reporting for Studies Conducted Under DMID Sponsored IND

Following notification from the investigator, DMID, the Investigational New Drug (IND) sponsor, will report any suspected AE that is both serious and unexpected. DMID will report an AE as a suspected AE only if there is evidence to suggest a causal relationship between the drug and the AE. DMID will notify FDA and all participating investigators (i.e., all investigators to whom the sponsor is providing drug under its IND(s) or under any PI's IND(s)) in an IND safety report of potential serious risks from clinical trials or any other source, as soon as possible, but in no case later than 15 calendar days after the sponsor determines that the information qualifies for reporting as specified in 21 CFR Part 312.32. DMID will also notify FDA of any unexpected fatal or life-threatening suspected AE as soon as possible, but in no case later than 7 calendar days after the sponsor's initial receipt of the information. Relevant follow up information to an IND safety report will be submitted as soon as the information is available. Upon request from FDA, DMID will submit to FDA any additional data or information that the agency deems necessary, as soon as possible, but in no case later than 15 calendar days after receiving the request.

All serious events designated as “not related” to the study drug, will be reported to the FDA at least annually in a summary format.

9.3.3 Other Adverse Events (if applicable)

9.3.3.1 Reporting of Overdose

An overdose is defined as a dose greater than the high-dose level evaluated in the trial as described in [Section 6.3.1](#) of the protocol. All overdoses should be reported; if the overdose is associated with an AE, then the AE should also be reported. In the event of an overdose of study drug, the investigator should use clinical judgment in treating the overdose and contact the DMID MM. The investigator should refer to the relevant document(s) for detailed information regarding warnings, precautions, contraindications, AEs, and other significant data pertaining to zoliflodacin. Such documentation may include but not be limited to the IB.

9.3.4 Reporting of Pregnancy

Pregnancies that occur in female subjects during the study period will be reported via AdvantageEDCSM on a pregnancy report form. With the subject’s permission, all protocol-required venous blood samples will be obtained and the subject will continue to be followed for safety until Final Visit. Efforts will be made to follow all pregnancies reported during the trial to pregnancy outcome, as described in the protocol-specific MOP (e.g., delivery, spontaneous abortion, or therapeutic abortion), pending the subject’s permission.

A female subject who participates in the trial and becomes pregnant will be asked to inform study personnel of a pregnancy occurring 30 days after the final study visit. A male subject who participates in the trial and whose female partner becomes pregnant 90 days after the final study visit will be asked to inform study personnel of the pregnancy. For all reported pregnancies, subjects will be asked to provide pregnancy outcome upon delivery or pregnancy termination to the CTU.

9.4 Type and Duration of Follow-up of Subjects after Adverse Events

Treatment-emergent SAEs and AEs will be followed until resolution or until considered stable in the clinical judgment of the investigator. Resolution of an AE is defined as the return to pretreatment status or stabilization of the condition in the clinical judgment of the study investigator, with the expectation that it will remain chronic.

Follow-up procedures, evaluations, and outcomes will be recorded in the subject's source document and eCRF.

9.5 Halting Rules

9.5.1 Study Halting Criteria

Study dosing must be stopped and a review of available safety data will be conducted by the SMC if any of the following occur on Day 1 after dosing:

1. Death of a subject following dosing regardless of relatedness to study drug;
2. One subject with an SAE that is considered related to study drug by the study PI or designated physician;
3. Two or more subjects with a Grade 3 systemic AE coded in the same organ system that is considered related to the study drug by the study PI or authorized clinician (listed in FDA Form 1572);

Note: VS abnormalities should be considered part of a systemic disorder or an organ-specific condition, as described in [Appendix C](#), in order to be included among the Study Halting Criteria.

4. An overall pattern of symptomatic, clinical non-serious events that the study PI or authorized clinician considers associated with study drug and that may appear minor in terms of individual events, but that may collectively represent a serious potential safety concern and pose a risk to continuing the subject in the trial.

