Halting Criteria Decision Process: If criteria for halting the trial (as listed in [Section 9.5.1](#)) are met during dosing on Day 1 prior to all subjects being dosed, an *ad hoc* Safety Monitoring Committee (SMC) meeting will be held to review all available safety data and to make recommendations about the dosing of all further subjects in the trial. A scheduled SMC meeting will be held after all subjects complete the trial to review all safety data, and advise on using the 4-g dose in a subsequent thorough QTc study.

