4 STUDY DESIGN

The trial will be performed as an open-label, non-randomized, single-dose design in eight healthy male or female subjects to evaluate the PK and safety profiles of the zoliflodacin formulation. All subjects will be dosed in the morning of Day 1 in a staggered fashion with a minimum of several minutes apart. Each subject will receive a single 4g dose of zoliflodacin (2 x 2 g sachets of zoliflodacin) after at least an 8-h fast, which will continue for at least 4 h after dosing. Consumption of water will be permitted during the fasting period. Subjects will be monitored as inpatients in the Clinical Trial Unit (CTU) up to Day 4 and at the Final Visit (Day 8 ± 2).

Subjects who consent to participate will be enrolled in the trial if they meet all inclusion and none of the exclusion eligibility criteria. Laboratory assessments at Screening Visit will include testing for serology (HIV, HBsAg, and HCV), drugs of abuse, and alcohol. Serum pregnancy testing will be done in all women and serum FSH levels will be measured only in post-menopausal women. Safety assessments at scheduled visits will include MH, VS, PE, 12-lead ECG, and clinical laboratory tests including CBC with differential, comprehensive metabolic (chemistry) panel, and UA. Treatment-emergent AEs and SAEs will be assessed from the time of dosing to the end of the trial. Plasma for PK analysis will be collected at scheduled time points before and after initiation of dosing on Day 1 and through Day 4, or ET.

Safety Monitoring and SMC Role

A SMC will be appointed to oversee the safe conduct of the trial. A scheduled SMC meeting will be held after all subjects complete the trial to review safety data, and advise on using the 4-g dose in a subsequent thorough QTc study. If criteria for halting the trial (as listed in [Section 9.5.1](#)) are met during dosing on Day 1, an *ad hoc* SMC meeting will be held to review all available safety data and to make recommendations about the dosing of all further subjects in the trial. An independent safety monitor (ISM), who is local to the CTU, will review SAEs and other severe safety signals and provide an independent analysis to the Site PI, SMC, and DMID.

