5 STUDY ENROLLMENT AND WITHDRAWAL

Only subjects who meet all inclusion criteria and none of the exclusion criteria will be eligible for enrollment into the trial. No exemptions are granted on Inclusion/Exclusion Criteria in DMID sponsored trials.

Eight healthy male and female subjects, aged 18 to 45 years inclusive, will be enrolled in a single cohort. Up to two alternates will be recruited.

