5.3.4 Handling of Withdrawals and Discontinuation of Administration

Subjects who are withdrawn before dosing may be replaced. Following dosing, one subject may withdraw before Day 4 without being replaced. A subject who cannot ingest the entire volume of drug suspension or a subject who took the entire dose but vomits up to 24 h after dosing will also be replaced. Subjects who ingest the entire volume of the initial [REDACTED] drug suspension but who do not ingest the content of the second [REDACTED] study drug suspension will not be withdrawn from the study or replaced. Subjects who received any amount of the study drug but withdraw from the trial will be encouraged to continue follow-up (with subjects' consent) for safety assessments and PK sample collection. Subjects withdrawing will be asked to complete a final termination visit if they do not wish to be followed per protocol.

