6.2 Dosage, Preparation, and Administration of Study Intervention/ Investigational Product

All subjects will receive a single 4-g PO dose (2 sachets of 2 g) of zoliflodacin in the morning of Day 1 in a staggered fashion several minutes apart.

The study drug will be inspected for damage, contamination, discoloration, or particulate matter before use. Any study drug that fails inspection should be quarantined at 2-8°C (35.6-46.4°F) and labeled 'Do Not Use' until further notice. The Site PI or responsible person should immediately contact the DMID Product Support Team at [contact] and DMID Clinical Project Manager (CPM) for further instructions before administering any additional study drug. Based on the information collected, DMID and/or Entasis will determine whether the affected study drug can be used. If it cannot be used, the site will receive specific instructions on how to return it to DMID CMS or destroy it on site.

A detailed procedure will be described in the MOP.

Eligible subjects who provide informed consent, undergo screening procedures, and qualify, meeting all inclusion and none of the exclusion criteria for the trial, will receive a single 4-g dose (2 sachets of 2 g of zoliflodacin reconstituted on the same day and administered in a total of [REDACTED] [REDACTED]) orally after an overnight fast. The dose will be administered in a standardized cup as described in the MOP. After the [REDACTED] of zoliflodacin is administered, an additional [REDACTED] [REDACTED] will be added to the same cup and consumed by the subject to chase the initial dose. Dosing should be completed within 5 minutes after each study product suspension. After dosing, subjects will continue to fast for an additional 4 h while water is allowed *ad lib*.

Refer to the protocol-specific MOP for detailed information on the preparation and administration of zoliflodacin.

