6.5 Assessment of Subject Compliance with Study Intervention/ Investigational Product/Device

Since each dose of zoliflodacin will be administered by site personnel, subject compliance is not anticipated to be an issue. Complete information regarding any partial or interrupted dosing will be documented. Subjects unable to ingest the full amount of the initial [REDACTED] of study drug suspension or who vomit within 24 h after dosing will be withdrawn from the study and replaced (See [Section 5.3.3](#) and [5.3.4](#)). Subjects who do not ingest the content of the second [REDACTED] study drug suspension will not be withdrawn from the study.

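### The mandatory dosing stop in Protocol 9.5.1 covers Day 1 events only, although a replacement for a subject who vomits late may fall due for dosing after Day 1

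*Protocol*

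**What the plan says.** **Halting rule.** Protocol 9.5.1 makes the stop in dosing and the SMC review compulsory "by the SMC if any of the following occur on Day 1 after dosing". The four criteria are any death; one related SAE; two or more subjects with related Grade 3 systemic events in the same organ system; and a worrying overall pattern of non-serious events.

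**Ad hoc SMC meeting.** The Protocol Summary is narrower and applies where the criteria "are met during dosing on Day 1 prior to all subjects being dosed". Sections 4 and 11.3 also tie the meeting to dosing on Day 1. Section 9.6.2 and SAP 6.6 name no day, but both rely on the criteria in 9.5.1.

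**Dosing.** Section 4: "All subjects will be dosed in the morning of Day 1 in a staggered fashion with a minimum of several minutes apart". Section 6.2 has the dose taken "orally after an overnight fast".

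**Replacement.** Section 5.3.4: "a subject who took the entire dose but vomits up to 24 h after dosing will also be replaced". Section 6.5, repeated in SAP 9.2, covers subjects "who vomit within 24 h after dosing will be withdrawn from the study and replaced". Section 5.3.4 also says: "Following dosing, one subject may withdraw before Day 4 without being replaced". This implies, without stating it, that a second such withdrawal would be replaced. Section 5 adds: "Up to two alternates will be recruited".

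**The concern.** A Day 1 limit suits a plan in which all eight subjects are dosed minutes apart on one morning, because after that morning there is no dosing left to stop. The replacement rule breaks that logic. It can create a new dose after the period in which the stop is compulsory.

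What is at stake is one further healthy volunteer. If an already dosed subject dies or has a related SAE on Day 2 or later while a replacement is waiting, the protocol does not itself hold that dose. The same event on Day 1 would.

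**Working it through.** The plan gives no figure to reproduce on this point. The check is a timeline and a comparison of sections.

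**1. Can a replacement fall due after Day 1?** Let the dose be given at clock time *h* on Day 1, with morning meaning *h* < 12. The vomiting trigger runs for 24 h from *h*.

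- Part after noon on Day 1: 24 − (12 − *h*) = 12 + *h* hours, so at least 12 h for any morning dose.
- Part on Day 2: 24 − (24 − *h*) = *h* hours.

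The documents give no clock time. For an assumed 07:00 to 10:00:

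| *h* | After noon on Day 1 or later | Of which on Day 2 |
|---|---|---|
| 7 | 19 h (19/24 = 79%) | 7 h |
| 10 | 22 h (22/24 = 92%) | 10 h |

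A replacement triggered after noon cannot be dosed on the morning of Day 1. One triggered after midnight cannot be dosed on Day 1 at all. These hours are lengths of the vomiting window. They are not uncovered risk time, because an event between noon and midnight on Day 1 is still caught by 9.5.1.

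**2. Does the meaning of Day 1 matter?**

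| Event | Day 1 = common dosing day | Day 1 = each subject's own dosing day |
|---|---|---|
| In an already dosed subject, on the planned dosing day | stop required | stop required |
| In a replacement, on the replacement's own later dosing day | not covered | stop required |
| In an already dosed subject, Day 2 or later, before a replacement is dosed | not covered | not covered |

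The last row is the gap, and it is the same on both readings.

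**3. What still applies after Day 1?**

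- *Required, no day limit:* SAE report to the sponsor within 24 h of site awareness, copied to the independent safety monitor, with medical-monitor assessment of the effect on subject safety and conduct (9.3.1); SMC review of related SAEs outside its periodic cycle (9.2.3); review of SAEs and severe signals by the independent safety monitor (Section 4, though 9.2.3 makes this as needed).
- *At discretion:* ad hoc SMC meeting at the sponsor's request (9.6.2); termination (5.3.6, 14.6). Section 14.6 bars further treatment only once the trial is discontinued.

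None of these stops dosing automatically.

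**4. How many doses?** 8 planned + up to 2 alternates = at most 10, so at most 2 replacement doses if only alternates are used. For an assumed per-subject risk *p* of vomiting within 24 h, independent across subjects, the chance of at least one such replacement is 1 − (1 − *p*)^8: 7.7%, 14.9%, 33.7% and 57.0% for *p* = 1%, 2%, 5% and 10%. This counts vomiting at any time in the 24 h and says nothing about a late qualifying event, whose probability the documents do not allow to be estimated.

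**The case against.** **No dosing after Day 1 is written down.** Every dosing statement refers to the morning of Day 1, and the Protocol Summary's enrollment time of up to 10 days, from dosing to last visit, reads as one dosing day. The alternates are not reserved for post-dose replacement; they may serve withdrawals before dosing. Detailed dosing steps are left to the manual of procedures and SMC procedures to the charter, neither of which is available here. This stands, so later dosing must be called an inference. It does not remove the point, because a compulsory replacement triggered after midnight cannot be met on Day 1.

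**Day 1 may be each subject's own day.** Section 7.4.1 can be read that way, and the replacement's own dosing day is then covered. That stands, and it narrows the gap without closing it.

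**Oversight continues.** A reader might infer that nothing protects subjects after Day 1, or that everything left is discretionary. The documents do not support that: SAE reporting, medical-monitor assessment and SMC review of related SAEs are required. Nor is investigator judgment what separates the two regimes, since criteria 2 to 4 of 9.5.1 rest on it too. The difference is the automatic stop once a criterion is met.

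**The practical risk is small.** One Phase 2 patient at 3 g vomited, the AEs reported in that trial were non-serious, and the 4-g dose of the earlier formulation was well tolerated. This supports a minor grading. It is not a reason to leave the wording as it is, since this trial gives 4 g of a new formulation.

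**Conclusion.** The gap is real and minor, and closing it is a cheap improvement. Section 9.5.1 does not compel a stop for a qualifying event on Day 2 or later in an already dosed subject while a replacement dose is pending, on either reading of Day 1. The conclusion rests on one inference: that a replacement for late vomiting would be dosed, and would be dosed after Day 1. It requires both a pending replacement and a late qualifying event, and harm would also require that the mandatory reviews failed to hold the dose. The uncovered time cannot be stated, because no replacement date is given. The PK estimates and the analysis are unaffected.

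**What to change.** In 9.5.1, after the words "by the SMC if any of the following occur on Day 1 after dosing", add: *or in any dosed subject at any later time before a replacement subject is dosed*. State that, once a criterion is met, no replacement is dosed until the SMC has reviewed. Existing Day 1 cover stays as it is; the window should not simply end at the last dose, which would remove cover for later Day 1 events.

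In the Protocol Summary, Section 4 and Section 11.3, delete the restriction to dosing on Day 1 (and in the Summary the clause about all subjects having been dosed). The ad hoc meeting then follows whenever the criteria are met, as 9.6.2 and SAP 6.6 already provide. SAP 6.6 needs no change. If no dosing after Day 1 is intended, 5.3.4 should say so instead.

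Cost: one clause, one sentence and three small deletions; a brief check before each replacement dose; and a possible delay to that dose if a criterion has been met. Sample size and analysis do not change.
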